## **INTRODUCTION**

*Peroxisome proliferator-activated receptor (PPAR)- $\gamma$  coactivator 1 alpha (PGC-1 $\alpha$ )* plays a role in many substantial metabolic processes, energy homeostasis and promotes muscle tissue remodeling, which is oxidative and less glycolytic (Liang & Bangsal, 2006). In conjunction with PGC-1 $\alpha$  on mitochondrial respiration (regulating respiration) in muscle cells, this co-activator also induces gene expression for the insulin sensitive glucose transporter (Glut-4) and increases glucose uptake (Puigserver & Spiegelman, 2003; S. Yang et al., 2020). PGC-1 $\alpha$  also induces brown adipose tissue (BAT) which usually declines in aging (Puigserver & Spiegelman, 2003). BAT which is a brown adipocyte contains many small droplets and a much higher number of mitochondria (containing iron), which gives the tissue its color (Cedikova et al., 2016). Brown fat also contains more capillaries than white fat and this supplies tissues with oxygen and nutrients and distributes the heat generated throughout the body (Cedikova et al., 2016). Noticing the function of PGC-1 $\alpha$  in the thermogenic brown adipose tissue (BAT) program, the regulation of Glut-4 and mitochondrial oxidation in the muscle, and the dominant role of PGC-1 $\alpha$  in hepatic gluconeogenesis along promoting muscle tissue remodeling activity, all of which suggest that this

co-activator can be a target for antiobesity, antidiabetic and antiaging drugs (Chronic Diseases and Aging) (Liang & Ward, 2006; Puigserver & Spiegelman, 2003; S. Yang et al., 2020).

Sea grape (*Caulerpa racemosa*) or lawi-lawi (local Indonesian term) is a species of green algae classified as *Caulerpaceae* family that had be found in the waters around Sulawesi (Pakki et al., 2020). Sea grapes are harvested intensively because they are an important source of macronutrients and micronutrients, especially in East and Southeast Asia (commercially grown in ponds and consumed in parts of the Philippines, Indonesia and Vietnam) as the main source of traditional diets (Chen et al., 2019), although it is still used for health products. Several studies have shown that sea grapes contain several bioactive components, such as protein, polysaccharides, polyphenols, flavonoids, and antioxidants (P. Yang et al., 2015; Yep et al., 2019; Taslim & Fahrul, 2021). In addition, sea grapes contain high antioxidant levels, and may be potential as functional foods or nutraceuticals (Tanna et al., 2020; Yep et al., 2019; Nurkolis et al., 2021). Doses of 150 mg/kg BW (30 mg/200g BW) sea grape extract in a previous pre-clinical trial, showed that it could improve blood glucose, total cholesterol and serum PGC-1 levels in rats fed a diet high in fat and cholesterol (Kuswari et al., 2021). In addition, you also have hepatoprotective activity (aka non-toxic) in diabetic mice (Qudus B Aroyehun et al., 2020). Previous research (Kuswari et al., 2021), is an in vivo (Pre-clinical) study that has not represented the benefits or efficacy of sea grape extract on variables tested in humans. Therefore, this clinical trial was conducted to support the effect of sea grape extract-antioxidant on blood glucose, total cholesterol, and PGC-1 levels in obese men for 4 weeks using a Randomized-Double Blind Controlled Trial.

## **Methods**

This clinical trial study was conducted at Manado City, Indonesia.

## **Extract Creation**

Fresh sea grape (*Caulerpa racemosa*) is collected from the shallows (5-10 meters above sea level) of Mantehage seawater, North Sulawesi, Indonesia. Botanical identification and authentication are confirmed in the department of pharmacology, faculty of mathematics and natural sciences, Sam Ratulangi University, Indonesia. Specimens are collected for future reference. Sea grapes (Whole body) is thoroughly rinsed with water, dried with air at room temperature, and in a 40° C oven, then smoothed with an electric grinding. Furthermore, the extract preparation, coarse powder (1 kg) is macerated in ethanol 96% for 72 hours with each extraction carried out in triple, which results in a yield of 34%. The extract is roughly filtered with Whatman 41 filter paper. The total filtrate is glued and evaporated at 40° C with the RV 8 IKA rotary evaporator under reduced pressure (100 millibars) for 90 minutes and evaporated in a 40°C oven to produce the viscous extract. The extract is stored in the refrigerator at a temperature of 10°C until used in research. The extract powder is encapsulated in capsules no. 000.

### **Dose Conversion**

The best and significant dose in a preliminary study (Pre-clinical) in Ratus novergicus rats is 150 mg/kg BW (Kuswari et al., 2021). Afterward, the doses in this clinical trial study applied the table (Table 1) "Evaluation of drug activities: pharmacometrics, ed. by D.R. Laurence and A.L. Bacharach" (Laurence & Bacharach, 2013). The conversion factor from mouse to human was 56.0. However, the dose is still within (mg/kg BW) while the conversion factor for rats must be per 200gram BW, so 150 divided (1000:200=5) then you get 30 mg/200gram BW. Therefore, it means:

$$\text{Human Dose} = \text{Rat Dose} \times \text{Conversion Factor} = 30 \times 56,0 = 1680 \text{ mg}/70\text{kg BW}$$

**= 1,68 g/70kg BW**

### **Antioxidant Test on Sea Grape Extract**

Antioxidant activity is determined by using DPPH (Batubara et al., 2015). Each sample consisting of 100 L was placed in microplate 96 and added 100 L DPPH 0.3 mM, then incubated for 30 minutes in a dark room. Sample absorption was measured using an ELISA reader at wavelength 517 nm. Antioxidant activity is calculated by equation 1 as follows:

$$\text{Inhibition (\%)} = \frac{(A_0 - A_1)}{A_0} \times 100\%$$

[figure not shown]
Explanation:

A0 = Blank Absorption, A1 = Standard or Sample Absorption

The results of the antioxidant activity test against DPPH resulted in a value of  $45.66 \pm 0.55\%$  (Triplicates/Triplo).

Caulerpin (PubChem ID: 5326018) with molecular formula: C24H18N2O4 is a typical secondary metabolite compound belonging to the algae genus *Caulerpa* Sp and is a bioactive compound from a group of alkaloid compounds that also functions as antioxidants (de Souza et al., 2009; Aguilar-Santos., 1970; Gorbi et al., 2014). Therefore, a further test was carried out, namely the antioxidant-caulerpin levels in the extract (sample) using Liquid Chromatography - Mass Spectrometry (LC-MS) and obtained 398.13278 Mass (397.12257 m/z). This shows that it is true that there is an antioxidant compound-caulerpin in the sample extract.

## Study Protocol with SAP and/or ICF

The study was a 4-week, randomized, double-blind, placebo-controlled clinical trial followed by a 1-week screening period. Participants who respond to the invitation and meet the entry criteria during the telephone screening interview are scheduled for the initial visit. Evaluation during the initial visit includes physical examination in the form of BMI (Body Mass Index) based on Asia-Pacific guidelines and blood parameter screening tests in the form of blood glucose, triglycerides, high-density lipoprotein (HDL), low-density lipoprotein (LDL) and total cholesterol, and PGC-1 $\alpha$  were performed on all participants within 1 week of the initial screening. A random number between 1 and 70 was generated for each subject and registered participants were scheduled for their first visit and randomly assigned to the sea grape extract group (n=35) or placebo (n=35). Sea grape extract/placebo tablets/capsules were given to participants every 1 week

(1 day of consumption per oral) 15 Minutes before eating (According to the diabetes drug guideline consumption).

During the 4-week intervention period, participants were asked to continue their usual diet and not to consume functional foods or other dietary supplements. Anthropometry (BMI), Waist Hip Ratio (WHR), blood parameters, urine profile (Marker of toxicity), and nutrient intake of both groups were measured before and after the intervention period. During the trial phase, all participants were instructed to maintain their normal diet and physical activity. Each week participants were asked to report assessments of side effects or changes in training, lifestyle, or diet; and to evaluate tablet compliance.

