### **Measurement of Efficacy Results**

A total of 70 participants who met the research criteria were asked to visit the clinic once every 1 week (0th, 1st, 2nd, 3rd, and 4th/last week of the study period) with a total of 5 clinical visits including initial examination. During each visit, the use of the supplement is currently reviewed and symptoms or side effects are noted. During screening visits, demographic and lifestyle information is collected (age, alcohol consumption, and smoking habits). Medical history is taken and urine turbidity tests are carried out.

The following parameters are assessed; Weight, Height, WHR and BMI during each visit. Blood samples were collected after a minimum of 12 hours of fasting during initial screening as

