well as in the 0, 2nd and 4th weeks of the intervention period to obtain blood glucose profiles, total cholesterol, triglycerides, high-density lipoprotein (HDL), low-density lipoprotein (LDL) and PGC-1 $\alpha$ . Blood samples were taken from the arm vein. The arm vein to be punctured is cleaned with 70% alcohol and allowed to dry. A tourniquet is placed on the upper arm to expose and slightly accentuate the veins. The skin is stretched over the vein with the fingers of the left hand so that the vein cannot move. The skin is pierced with a needle and syringe with the right hand until the tip of the needle enters the lumen of the vein. The tourniquet is removed and slowly withdraw the syringe suction until the desired amount of blood is obtained. A 70% alcohol swab is placed over the needle and the syringe and needle are removed. The needle is removed from the syringe and the blood sample is transferred into a vacutainer tube. The sample is then centrifuged for 20 minutes at a speed of 3000 rpm. Finally, the serum is collected for analysis of blood glucose, total cholesterol, triglycerides, high-density lipoprotein (HDL), low-density lipoprotein (LDL) and PGC-1 $\alpha$ . Blood glucose, triglycerides, high-density lipoprotein (HDL), low-density lipoprotein (LDL) and cholesterol levels were tested using COBAS Integra® 400 plus analyzer (Roche). The sample was washed with Phosphate Buffered Saline (PBS, pH 7.4) 1% until the liquid was clear. The sample was centrifuged at 3000 rpm for 20 minutes to obtain pellets and supernatants. The supernatant is taken for PGC-1 $\alpha$  examination. The concentration of PGC-1 $\alpha$  is measured using the Human PGC-1 $\alpha$  (PGC1 alpha (PPARGC1A) (NM\_013261) Human Untagged Clone kit.

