### **Statistical Analysis**

Statistical analysis is performed using SPSS software, version 26 (IBM Corporation). Fixed effects include treatment groups, treatment visits, and interactions between treatment and visit groups. The value  $p < 0.05$  is considered statistically significant.

Table 1. Dose Conversion of Experimental Animals with Humans

	Mice 20 g	Rat 200 g	Guinea Pig 400 g	Rabbit 1,5 kg	Cat 2 kg	Ape 4 kg	Dog 12 kg	Human 70 kg
Mice 20 g	1,0	7,0	12,25	27,8	29,7	64,1	124,2	387,9
Rat 200 g	0,14	1,0	1,74	3,9	4,2	9,2	17,8	56,0
Guinea Pig 400 g	0,08	0,57	1,0	2,25	2,4	5,2	10,2	31,5
Rabbit 1,5 kg	0,04	0,25	0,44	1,0	1,08	2,4	4,5	14,2
Cat 2 kg	0,03	0,23	0,41	0,92	1,0	2,2	4,1	13,0
Ape 4 kg	0,016	0,11	0,19	0,42	0,45	1,0	1,9	6,1
Dog 12 kg	0,008	0,06	0,10	0,22	0,24	0,52	1,0	3,1
Human 70 kg	0,0026	0,018	0,031	0,07	0,076	0,16	0,32	1,0

KOMITE ETIK PENELITIAN KESEHATAN  
*HEALTH RESEARCH ETHICS COMMITTEE*  
RSUP PROF. DR. R. D. KANDOU MANADO  
*RSUP PROF. DR. R. D. KANDOU MANADO HOSPITAL*

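### The blood-sampling schedule is stated in conflicting ways, and the analysis model does not say which visits enter, how the pre-treatment value is used or which contrast tests efficacy

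*Combined protocol and SAP*

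**What the plan says.** The schedule is described twice. Under Study Protocol with SAP and/or ICF, "blood parameters, urine profile (Marker of toxicity), and nutrient intake of both groups were measured before and after the intervention period". Under Measurement of Efficacy Results, fasting blood is drawn at the screening stage and then at later points, given as "well as in the 0, 2nd and 4th weeks of the intervention period", and the outcomes listed are glucose, the lipids and PGC-1α.

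Whether screening and week 0 are separate is not settled. The same efficacy section lists clinic visits at weeks 0, 1, 2, 3 and 4, "with a total of 5 clinical visits including initial examination". Weeks 0 to 4 are already five visits. Yet the general description says that the full blood panel, PGC-1α included, is among the tests that "were performed on all participants within 1 week of the initial screening", and it mentions a first visit and random assignment after that.

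The Statistical Analysis section gives one sentence on the model: "Fixed effects include treatment groups, treatment visits, and interactions between treatment and visit groups". It adds the software and a 0.05 significance threshold. It does not list the visits that enter, say whether pre-treatment values are responses or covariates, or name the term or week that tests efficacy.

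**The concern.** In a model built on visit and group-by-visit, the sampling schedule defines the test. Two, three or four visit levels give interaction tests with 1, 2 or 3 numerator degrees of freedom, and so different p-values from the same men. The group main effect is a further candidate. With none of this fixed, the choice can be made after the results are known.

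There is also a question of efficiency. A pre-treatment value entered as one more response makes the group main effect average over a time when the true difference is zero. Entered as a covariate, the same value would remove part of the between-man variation. With 70 men and no sample-size justification in the document, that difference matters.

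**Working it through.** The plan states no power, effect size or SD, so there is no figure of its own to reproduce.

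**Inputs from the document.** n = 35 per arm ("sea grape extract group (n=35) or placebo (n=35"); threshold 0.05, taken as two-sided; visit sets as described above.

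**Assumed inputs, not in the document.** Week-4 effect d = 0.5 SD; correlation ρ = 0.6 between any two visits of the same man (compound symmetry); complete data; week-2 effect equal to none, half or all of d.

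**Formulas, for J visit levels with true differences δ₁…δ_J.**
- Main effect as a share of the week-4 effect: mean(δ)/d.
- Main-effect variance: (2/n) × [1 + (J−1)ρ]/J. Noncentrality: mean(δ)²/variance, df 1, 68.
- Interaction noncentrality: (n/2) × Σ(δⱼ − mean δ)²/(1−ρ), df J−1, 68(J−1).
- Week-4 difference adjusted for baseline: noncentrality (n/2) × d²/v, where v = 1 − ρ² with one baseline value and v = 1 − 2ρ²/(1+ρ) with the mean of two.

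**Worked case: weeks 0, 2, 4 with half the effect at week 2.** δ = 0, 0.25, 0.50, so the mean is 0.25 and the share 50%. Main-effect variance = (2/35) × 2.2/3 = 0.0419; noncentrality = 0.0625/0.0419 = 1.49; power 22.6%. Interaction: Σ = 0.125; noncentrality = 17.5 × 0.125/0.4 = 5.47; df 2, 136; power 53.3%.

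| Visits as responses | Interaction df | Week-2 effect | Main effect, share of week-4 effect | Main-effect power | Interaction power |
|---|---|---|---|---|---|
| 0, 4 | 1, 68 | not used | 50% | 21.1% | 63.5% |
| 0, 2, 4 | 2, 136 | none | 33% | 12.6% | 66.4% |
| 0, 2, 4 | 2, 136 | half | 50% | 22.6% | 53.3% |
| 0, 2, 4 | 2, 136 | full | 67% | 36.2% | 66.4% |
| screening, 0, 2, 4 | 3, 204 | none | 25% | 9.5% | 65.7% |
| screening, 0, 2, 4 | 3, 204 | half | 37.5% | 15.2% | 61.5% |
| screening, 0, 2, 4 | 3, 204 | full | 50% | 23.4% | 79.3% |

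The lowest interaction figure becomes 52% if the error df is held at 68.

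**Baseline as covariate.** One value: v = 1 − 0.36 = 0.64; noncentrality = 17.5 × 0.25/0.64 = 6.84; power 73%. Mean of two: v = 1 − 0.72/1.6 = 0.55; noncentrality = 17.5 × 0.25/0.55 = 7.95; power 79%. Neither depends on the week-2 effect.

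**Range for the correlation.** With ρ = 0.5 and 0.7, one-baseline power is 66% and 82%, two-baseline power 71% and 89%, and the before/after interaction 54% and 76%. The second baseline value cuts residual variance by 11% at ρ = 0.5, 14% at 0.6 and 17% at 0.7.

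**The case against.** The strongest reply is that the before-and-after sentence is a loose summary and the efficacy section is the operative schedule. Staff who follow the named weeks collect every sample that the summary needs. That is a fair reading for sample collection. It does not tell the analyst which draws enter the model, and the Statistical Analysis section does not say either.

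A reader might also infer that the schedule conflict itself dilutes the treatment effect. The documents do not support this. Plain before/after already halves the main effect, and weeks 0, 2 and 4 give 50% too, or 67% if the effect is complete by week 2. The loss comes from treating a baseline value as a response and testing the main effect. The plan commits to neither. It also lists the interaction, which is the usual efficacy term when baseline is a response and is not diluted in this way; its power can rise when a second pre-treatment draw is added.

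The term for visits in the model could be read as covering only visits on treatment. Then pre-treatment dilution disappears. But that reading is undefined, and with only weeks 2 and 4 in the factor the interaction is no longer an efficacy test: if the effect is full at both weeks, its power is just the 5% error rate.

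It is also tempting to say that the precision of two baseline draws is lost. The plan is silent on baseline handling, and screening and week 0 may be a single draw.

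**Conclusion.** The point stands as a gap in specification. The blood schedule is given in two ways, the separation of screening from week 0 is unclear, and the model leaves open the visit levels (two to four), the role of the pre-treatment value and the tested term. If the group main effect is tested with pre-treatment visits as responses, it estimates about 25–67% of the week-4 effect. These shares depend only on the week-2 effect and on whether screening enters.

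The power figures are illustrations that rest on the assumed effect, correlation, compound symmetry and complete data. On those assumptions, the week-4 difference adjusted for one baseline value (73%) is ahead of the main effect in every case (10–36%) and of the interaction for before/after or weeks 0, 2, 4 (52–66%). It is not ahead everywhere: the four-level interaction reaches 79% if the full effect is present by week 2, about the same as adjusting for two baseline values.

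**What to change.** 1. Reconcile the general study description and the efficacy section to one blood schedule and one visit count, and say whether screening and week 0 are separate draws.
2. Define baseline as the week-0 value, or as the mean of screening and week 0 if these are separate, and enter it as a covariate.
3. Keep only the post-treatment visits, weeks 2 and 4, in the visit factor.
4. Name the week-4 between-group difference from that model as the efficacy contrast. This step is needed with step 3, because the group-by-visit test over weeks 2 and 4 alone does not test efficacy.

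The cost is wording in two sections and the analysis paragraph, with no added men or blood draws. The gain from two baseline values is available only if both draws exist; the single-baseline version needs nothing beyond the week-0 sample already planned.

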### **Subjects/Participants**

The study participants were recruited during 2021 at RSUP [name]. RD. Kandou (Manado, Republic of Indonesia). A total of 150 participants agreed to participate in the study. Only individuals men who are obese ( $BMI \geq 25 \text{ kg m}^{-2}$  and Waist Hip Ratio (WHR)  $\geq 0.90$ ) according to Asia-Pacific guidelines and have not been diagnosed with other diseases were included in the study. To meet guidelines for evaluating the efficacy of functional food referring to the Korea Food and Drug Administration (because Indonesia does not yet exist and Korea belong to one Asian region so used) (KFDA Guideline, 2021), very obese participants ( $BMI \geq 30 \text{ kg m}^{-2}$ ) were not included in the study.

In total, 70 participants met the research criteria (age  $29.98 \pm 3.26$  year; weight,  $\dots \pm \dots$  kg; BMI,  $\dots \pm \dots \text{ kg m}^{-2}$ ) and were randomly divided into two groups ( $n = 35$  each) given sea grape extract  $1.68 \text{ g}/70\text{kg BB day}^{-1}$  or placebo ( $1.68 \text{ g}/70\text{kg BB day}^{-1}$ ). The exclusion criteria for this study are as follows: (a) significant weight variation (over 10%) in the last 3 months; (b) a history of cardiovascular disease including arrhythmia, heart failure, or myocardial infarction, diabetes

mellitus (DM) and the use of pacemakers; (c) a history of conditions that may interfere with test products or inhibit their absorption such as gastrointestinal diseases (Crohn's disease) or surgeries that have been experienced (caesarean section or enterocele); (d) participation in other clinical trials in the last 2 months; (e) abnormal liver function; (f) a history of kidney disease (eg, acute or chronic renal failure and nephritic syndrome); (g) undergo antipsychotic drug therapy within the last 2 months; (h) laboratory test results as well as medical or psychological conditions that may interfere with successful participation in research assessed by researchers; (i) a history of alcohol or substance abuse; and (j) allergy or hypersensitivity to any of the ingredients in the test product; (k) is neither a passive nor an active smoker. All participants give written consent before the investigation begins. The research protocol was submitted to the Health Research Ethics Commission (KEPK) of The General Hospital of Education [name]. RD. Kandou (Manado, Republic of Indonesia) online at <http://sim-epk.keppkn.kemkes.go.id>. All protocols referred to The Declaration of Helsinki and The Council for International Organizations of Medical Sciences (CIOMS).

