### **Evaluation of Safety and Diet**

The safety of the extract is assessed by the following procedure. Urine Test Strips 10 Verify Parameters, Parameters examined are:

- Glucose (50 -100 mg / dl)
- Protein (7.5 - 15 mg / dl)

- pH (5-9)
- Leukocytes (9-15 leu / ul)
- Nitrite (0.05-0.1 mg/ dl)
- Urobilinogen (0.2-1.0 mg / dl)
- Blood (5-10 Ery/ul)
- Ketones (2.5-5 mg/dl)
- Bilirubin (0.4-1.0 mg/ dl)
- Specific Gravity (SG) (1,000-1,030)

Test the urine parameters above using *Urinalysis 10U Reagent Strips Verify* (REF U031-102 exp. 2022-03-05). Pulse rate and blood pressure are measured on each visit after a 5-minute break using intelliVue MP70 (Philips, Netherlands). Personal reports are also recorded at these times. We kept the subjects maintaining their usual diet and activity, and all participants completed diet records on each visit to the clinic during the intervention period to evaluate their energy intake and diet quality. Food intake data were analyzed by a nutritionist ([name], S.Gz).

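### Exclusion (e), abnormal liver function, has no planned blood test behind it, and no transaminase or serum creatinine is measured after dosing, so biochemical liver or kidney changes would go largely undetected

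*Combined protocol and SAP*

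**What the plan says.** **Eligibility.** The exclusion list in Subjects/Participants includes "e) abnormal liver function; (f) a history of kidney disease". No test or threshold is attached to the liver criterion. The kidney criterion in full is "f) a history of kidney disease (eg, acute or chronic renal failure and nephritic syndrome". A general criterion also allows exclusion for "h) laboratory test results as well as medical or psychological conditions that may interfere with successful participation in research assessed by researchers", without naming any test.

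**Screening.** Study Protocol with SAP and/or ICF lists "blood parameter screening tests in the form of blood glucose, triglycerides, high-density lipoprotein (HDL), low-density lipoprotein (LDL) and total cholesterol", plus PGC-1α. Measurement of Efficacy Results adds medical history and a urine turbidity test at screening.

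**Blood during the trial.** Measurement of Efficacy Results has fasting blood taken at initial screening, as "well as in the 0, 2nd and 4th weeks of the intervention period to obtain blood glucose profiles, total cholesterol, triglycerides", HDL, LDL and PGC-1α. The serum goes to a chemistry analyser: "cholesterol levels were tested using COBAS Integra".

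**Safety.** Study Protocol with SAP and/or ICF has a "urine profile (Marker of toxicity") measured before and after the intervention in both groups. Evaluation of Safety and Diet opens with "The safety of the extract is assessed by the following procedure" and then describes a 10-parameter urine strip that includes bilirubin, urobilinogen, protein, blood and specific gravity. Pulse, blood pressure and personal reports are recorded at visits. Statistical Analysis describes no safety analysis.

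**The concern.** The protocol sets an entry condition on liver function and names toxicity as something it measures, but the named blood tests address neither. Two things follow.

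- **Entry.** A man with an undiagnosed liver abnormality could be enrolled against the protocol's own criterion, because nothing in the named screening panel is aimed at finding it.
- **Safety.** A rise in transaminases or serum creatinine in men taking the extract would not be recorded. A later statement that the extract was safe would then go beyond the data.

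The human dose is scaled from rats (Dose Conversion), and the Introduction's support for absence of toxicity is a study in diabetic mice. The documents therefore bring no human organ-safety data that could stand in for a measurement in this trial.

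**Working it through.** The plan gives no event rate, power or safety calculation to reproduce. The main check is to set the named tests against the two purposes.

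**Step 1: tests against purposes**

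- Blood analytes at screening: glucose, triglycerides, HDL, LDL, total cholesterol, PGC-1α. Liver or kidney analytes: 0 of 6.
- Blood analytes at weeks 0, 2 and 4: the same six. Liver or kidney analytes: 0 of 6.
- Other screening checks: medical history and urine turbidity. History can pick up known liver disease but not a silent abnormality.
- Urine strip: bilirubin and urobilinogen bear indirectly on the liver; protein, blood and specific gravity bear indirectly on the kidney. It is planned before and after the intervention, but the text does not tie it to screening or to criterion (e).
- Criterion (f) asks for a history, so medical history is enough to apply it. The entry gap is confined to (e).

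**Step 2: what 35 treated men could show**

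Input: 35 men on extract (Study Protocol with SAP and/or ICF).

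If no event is seen among n men, the exact one-sided 95% upper limit for the true rate is 1 − 0.05^(1/n). With n = 35:

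1 − 0.05^(1/35) = 0.082, or 8.2%.

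The chance that at least one of 35 men has an event of true rate p is 1 − (1 − p)^35. The rates below are assumptions, since the documents give none:

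- p = 1%: 30%
- p = 3%: 66%
- p = 5%: 83%
- p = 10%: 97%

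The 8.2% limit comes from the arm size and applies to whatever is measured. It can be stated for new bilirubin, protein or blood on the strip. It cannot be stated for transaminase or creatinine changes, because an event that no test measures is not recorded even if it occurs.

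**Step 3: cost of closing the gap**

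Inputs: 70 men randomised and 150 who agreed to take part (Subjects/Participants); three assays; two time points (screening and week 4).

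- Lower end, only the 70 reach the screening draw: 70 × 3 + 70 × 3 = 420 assays.
- Upper end, all 150 are bled at screening: 150 × 3 + 70 × 3 = 450 + 210 = 660 assays.

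The documents do not say how many of the 150 reached the blood draw, so the figure is a range.

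**The case against.** The strongest reply is that the plan is not empty on either count. The strip carries bilirubin, urobilinogen, protein and blood. Entry requires men with no other diagnosed disease, medical history is taken, and researchers may exclude on laboratory results. Reading (e) as requiring a test is an inference from its wording: unlike (f), it does not ask for a history. The stated aim is also glucose, cholesterol and PGC-1α, so the efficacy comparison is not shown to be affected.

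Much of this stands, and it rules out some stronger readings that a reader might infer:

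- **That no bound at all could be given for liver or kidney laboratory toxicity.** The strip findings are laboratory data and can be bounded. Monitoring is weak, not absent.
- **That criterion (e) cannot be applied by any route.** History and the researchers' general discretion remain. What is missing is a named test able to find a silent abnormality.
- **That the kidney exclusion fails too.** It is by history and works as written; for the kidney, the point concerns monitoring after dosing only.
- **That affected men were enrolled, or that the extract is harmful.** Nothing in the documents shows either.

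Feasibility is also a fair challenge. Recruitment is described in the past tense, and neither spare serum volume nor serum storage is mentioned. If screening is over, new assays can be used to apply (e) only if serum was kept.

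The reply does not close the gap. The general laboratory criterion names no test, and the only specified panel has no liver or kidney analyte. The strip measures neither transaminases nor serum creatinine. Toxicity remains a question that the protocol itself says it assesses.

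**Conclusion.** The point holds in this form: criterion (e) has no planned blood test to apply it, and organ safety after dosing rests on a urine strip, pulse, blood pressure and reported symptoms. Biochemical liver or kidney changes would be largely undetected, and only strip-level findings could be bounded, at best by 8.2% if none occurred in 35 treated men. Serum assays would not tighten that limit; they would let it be stated for the changes that now go unmeasured.

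The effect is on who may be enrolled and on what may be concluded about safety. No effect on the efficacy comparison is shown. The conclusion rests on reading (e) as a current state and on the named analytes being the whole blood panel, and it is limited to the protocol text available for review.

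**What to change.** 1. Add ALT, AST and creatinine to the analyser run on the fasting serum already drawn at screening, so that (e) can be applied before randomisation, and at week 4. The investigators set the cut-offs.
2. Report, by arm, the change from baseline and the number of men who shift from normal to abnormal, with exact confidence limits.
3. If the assays cannot be added, or screening is already complete, state how (e) was ascertained and limit any safety conclusion to urine-strip findings, pulse, blood pressure and reported symptoms.

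Items 1 and 2 cost a short amendment and about 420 to 660 routine assays, with no extra visit or needle, provided enough serum remains. The downside is a small laboratory cost and possibly a few more screen failures. Item 3 needs only a change of text.
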